12.3 Method of Treatment Assignment

Each subject will be assigned a unique identification number upon screening. Subjects who complete the study screening assessments and meet all the eligibility criteria will be assigned a unique randomization identification number at the time of the first dose, different from the screening number, and will receive the corresponding product, according to a randomization scheme generated at Celerion.

Subjects will receive each treatment on one occasion. The sequences to be used in the randomization will be ABCD, ABDC, BACD, and BADC. Every attempt will be made to include the same number of females in each sequence and the same number of males in each sequence.

If replacement subjects are used, the replacement subject number will be 100 more than the original (e.g., Subject No. 101 will replace Subject No. 001).

12.4 Blinding

This is an open-label study.

12.5 Treatment Compliance

A qualified designee will be responsible for monitoring the administration of the timed oral doses. A mouth check will be performed by the qualified designee to ensure that the subjects have swallowed the study drug. Once a subject has finished the dosing water, the qualified designee will use a flashlight and a tongue depressor to check the subject's mouth. Subjects' hands will also be verified to ensure that the study drug(s) was/were ingested.

13 STUDY ASSESSMENTS AND PROCEDURES

The Study Events Flow Chart ([Section 6](#)) summarizes the clinical procedures to be performed at each visit. Individual clinical procedures are described in detail below. Additional evaluations/testing may be deemed necessary by the PI or designee and/or the Sponsor for reasons related to subject safety.

For this study, the blood collection for LOXO-292 is the critical parameter and needs to be collected as close to the exact time point as possible. All other procedures should be completed as close to the prescribed/scheduled time as possible, but can be performed prior or after the prescribed/scheduled time.

Any nonscheduled procedures required for urgent evaluation of safety concerns take precedence over all routine scheduled procedures.

13.1 Screening

Within 28 days prior to the first dose, medical history and demographic data, including name, sex, age, race, ethnicity, body weight (kg), height (cm), BMI (kg/m²) and history of tobacco use will be reported. Each subject will have a physical examination, vital sign measurements (heart rate, blood pressure, temperature, and respiratory rate), 12-lead ECG, and the laboratory tests of hematological, coagulation, hepatic and renal function and additional tests as noted in [Section 13.2.6](#).

13.2 Safety Assessments

13.2.1 Physical Examination

Full and abbreviated physical examinations will be performed as outlined in the Study Events Flow Chart ([Section 6](#)).

An abbreviated physical examination will include at a minimum, examination of respiratory, cardiovascular, and gastrointestinal systems, with the option for further examination of additional systems as necessary based on reported symptoms/AEs.

Symptom-driven physical examinations may be performed at any time, if deemed necessary by the PI or designee.

13.2.2 Vital Signs

Single measurements of body temperature, respiratory rate, blood pressure and heart rate, will be measured as outlined in the Study Events Flow Chart ([Section 6](#)). Additional vital signs may be taken at any other times, if deemed necessary.

Blood pressure and heart rate measurements will be performed with subjects in a seated position, except when they are supine or semi-reclined because of study procedures and/or AEs (e.g. nausea, dizziness) or if deemed necessary by the PI or designee.

Blood pressure, heart rate and respiratory rate will be measured within 24 hours prior to Day 1 dosing for the predose time point. At all other predose time points, blood pressure, heart rate, and respiratory rate will be measured within 2 hours prior to dosing. When scheduled postdose, vital signs will be performed within approximately 15 minutes of the scheduled time point.

13.2.3 ECG Monitoring

Single 12-lead ECGs will be performed as outlined in the Study Events Flow Chart ([Section 6](#)). Additional ECGs may be taken at any other times, if deemed necessary by the PI or designee.

ECGs will be performed with subjects in a supine position. All ECG tracings will be reviewed by the PI or designee.

ECGs will be measured within 24 hours prior to Day 1 dosing of each period for the predose time point. At all other predose time points, ECGs will be collected within 2 hours prior to dosing. When scheduled postdose, ECGs will be performed within approximately 20 minutes of the scheduled time point.

13.2.4 Body Weight

Body weight (kg) will be reported as outlined in the Study Events Flow Chart ([Section 6](#)).

13.2.5 *Helicobacter pylori* Breath Test

The presence or absence of *Helicobacter pylori* will be determined as outlined in the Study Events Flow Chart ([Section 6](#)). A positive test is not to be used as an exclusionary criterion. The test results will be reported and may be used to explain aberrant PK results.

13.2.6 Clinical Laboratory Tests

All tests listed below will be performed as outlined in the Study Events Flow Chart (Section 6). In addition, laboratory safety tests may be performed at various unscheduled time points, if deemed necessary by the PI or designee.

Hematology

- Hemoglobin
- Hematocrit
- Total and differential leukocyte count
- Red blood cell count
- Platelet count

Coagulation

- Prothrombin Time/International normalized ratio
- Activated partial thromboplastin time

Serum Chemistry*

- Blood Urea Nitrogen
- Bilirubin (total and direct)
- ALP
- AST
- ALT
- Albumin
- Sodium
- Potassium
- Magnesium
- Chloride
- Glucose (fasting)
- Creatinine**
- Cholesterol
- Triglycerides
- Phosphorus
- Creatine kinase
- Amylase
- Lipase

Urinalysis

- pH
- Specific gravity
- Protein***
- Glucose
- Ketones
- Bilirubin
- Blood***
- Nitrite***
- Urobilinogen
- Leukocyte esterase***

Additional Tests

- HIV test
- HBsAg
- HCV
- Urine drug screen
 - Opiates
 - Opioids (methadone, oxycodone, and fentanyl)
 - Amphetamines
 - Barbiturates
 - Benzodiazepines
 - Cocaine
 - Cannabinoids
- Urine alcohol screen
- Serum pregnancy test (for females only)
- FSH (for postmenopausal females only)
- Thyroid stimulating hormone

* Samples for serum chemistry will be obtained following a fast of at least 12 hours at screening and at check-in; at other scheduled times, serum chemistry tests will be performed after at least an 8 hour fast. However, in case of dropouts or rechecks, subjects may not have fasted for 12 or 8 hours prior to the time that the serum chemistry sample is taken.

** At screening, creatinine clearance will be calculated using the Cockcroft-Gault formula.

*** If urinalysis is positive for protein, blood, nitrite and/or leukocyte esterase, a microscopic examination (for red blood cells, white blood cells, bacteria, casts, and epithelial cells) will be performed.

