Potential effects of LOXO-292 on the central nervous system were evaluated as part of the GLP 28-day repeat-dose study in rats, in functional observational battery tests and locomotor activity assessments. Findings were limited to animals receiving the high dose on week 4 of the dosing phase, and were attributed to poor general body condition and weight changes associated with LOXO-292 administration rather than specific neurological effects. Additionally, no microscopic abnormalities in neuronal tissues were found.

In toxicology studies of LOXO-292 that were conducted in the rat and minipig, the primary pathologic findings for both species were in the tongue, pancreas, bone marrow and lymphoid tissues; while the gastrointestinal tract and ovaries were target tissues in minipig. Other target tissues identified in the rat included: multi-tissue mineralization, phyeal cartilage, incisor teeth, lung, Brunner's gland, and possibly liver. Assessment of doses associated with moribundity/death revealed a steep dose response curve for both species.

LOXO-292 was not mutagenic in the GLP bacterial mutation assay. LOXO-292 was not found to be phototoxic when evaluated in an in vitro neutral red uptake phototoxicity assay.

Based on preclinical pharmacology experiments with human cancer cells in vitro and in murine xenograft models, meaningful inhibition of RET in tumors is expected to be achievable with oral dosing regimens ≥ 40 mg/day.

Based on the nonclinical profile, including results from animal toxicology studies, theoretical risks of human exposure to LOXO-292 include the following: loss of appetite, decrease in body weight, increase in total white blood cells, neutrophils, and monocytes, decrease in albumin, increase in globulin, decreased albumin:globulin ratio, decrease in total protein, increased body temperature, lethargy, increase in cholesterol and triglycerides, increase in phosphorus, changes in taste sensation and/or development of xerostomia, gastrointestinal symptoms/signs: nausea, vomiting, loose stools, abdominal discomfort, decreases in red cell mass (red blood cells, hemoglobin, hematocrit) and reticulocytes, decrease in platelets, increases in liver function tests (alkaline phosphatase, aspartate aminotransferase and alanine aminotransferase).

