## 7. SAFETY

No inferential statistics are to be performed for the safety analysis.

All clinical safety and tolerability data will be listed by subject and assessment time points, including rechecks, unscheduled assessments, and early termination (ET), chronologically.

Continuous variables will be summarized using n, arithmetic mean, SD, minimum, median, and maximum. Frequency counts will be reported for categorical data when appropriate.

The level of precision will be presented as follows: “n” as an integer, minimum/maximum in same precision as in the database, mean/median in one more precision level than minimum/maximum, and SD in one more precision level than mean/median.

Where individual data points are missing because of dropouts or other reasons, the data will be summarized based on reduced denominators.

When change from baseline is calculated, baseline is the last scheduled assessment before dosing of LOXO-292 at each period, including rechecks and unscheduled assessments, whichever is later, unless otherwise specified in the sections below. Rechecks, unscheduled assessments and ET measurements taken after first dosing will not be used in the summarization.

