For all laboratory values that are numeric, descriptive statistics (n, mean, SD, minimum, median, and maximum) will be presented for each laboratory test by treatment and time point. Change from baseline (defined below) will also be summarized. In general, postdose unscheduled events or rechecks will not be summarized. Similarly, ET results will not be included in summaries.

For each laboratory test, a shift table will be developed comparing the frequency of the results at baseline (above normal, normal, or below normal) to postdose results for

each part, respectively. For urinalysis tests, the categories are normal and outside normal.

Baseline is Day -1 of Period 1 and Day 7 of previous period for Period 2, 3, 4 and is the last non-missing predose measurement prior to dosing of LOXO-292, including rechecks and unscheduled assessments. Day 7 measurement of Period 1, 2, 3 might be used twice as postdose value of Period 1, 2, 3 and baseline value of Period 2, 3, 4. When serving as baseline of Period 2, 3, 4, the re-check or unscheduled values after Day 7 of Period 1, 2, 3 and prior to LOXO-292 dosing of Period 2, 3, 4 could be used as baseline.

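### A non-fasted recheck can become the chemistry baseline but in general stays out of the postdose summaries, so triglyceride and glucose changes can mix fasting states

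*Protocol*

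**What the plan says.** Protocol 13.2.6, in the footnote to serum chemistry, sets two fasting minimums: "Samples for serum chemistry will be obtained following a fast of at least 12 hours at screening and at check-in", and "at other scheduled times, serum chemistry tests will be performed after at least an 8 hour fast". Glucose is listed there as a fasting test. The same footnote makes an exception: "However, in case of dropouts or rechecks, subjects may not have fasted for 12 or 8 hours prior to the time" of sampling. The notes to both flow charts in Protocol Section 6 repeat the exception.

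SAP Section 7 gives the general rule that "baseline is the last scheduled assessment before dosing of LOXO-292 at each period, including rechecks and unscheduled assessments, whichever is later", unless a later section says otherwise. SAP 7.4 does so for laboratory tests. Baseline is Day -1 in Period 1 and Day 7 of the preceding period in Periods 2 to 4, and it "is the last non-missing predose measurement prior to dosing of LOXO-292, including rechecks and unscheduled assessments". It adds expressly that a recheck or unscheduled value taken after that Day 7 and before the next LOXO-292 dose may be the baseline. On the postdose side SAP 7.4 says: "In general, postdose unscheduled events or rechecks will not be summarized". Early-termination results are left out as well.

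Protocol 8.1.1 includes "increase in cholesterol and triglycerides" among the theoretical risks of LOXO-292.

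**The concern.** The samples that may be non-fasted are treated differently before and after dosing. Before dosing, a recheck is accepted, and it displaces the fasted scheduled value whenever it is later. After dosing, rechecks and early-termination samples are in general dropped. For a test that depends on fasting, the reported change can then be a fasted value minus a non-fasted one.

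The tables exposed are the change-from-baseline summary (Table 14.3.5.1) and the shift table (Table 14.3.5.2). Triglycerides matter most because an increase is a stated theoretical risk. Glucose is not named as a risk, but the protocol defines it as a fasting measurement, so a non-fasted baseline departs from its own specification.

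**Working it through.** The documents state no figure on this point and the sample size is redacted, so there is nothing to reproduce. The check traces the rules and then sizes the effect over assumed values.

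**1. The rules side by side**

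| Sample | Fast | Can be baseline? | In postdose summaries? |
|---|---|---|---|
| Scheduled | 12 h or 8 h | Yes | Yes |
| Recheck | May be waived | Yes, if last before the dose | In general no |
| Unscheduled | No rule stated | Yes, if last before the dose | In general no |
| Early termination | May be waived | Not applicable | No |

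The Day 7 sample shows the asymmetry. The scheduled value serves as a postdose value of one period and, by default, as baseline of the next. A recheck of it can take over only the baseline role.

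**2. Time available for a replacement**

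From the last scheduled chemistry to the LOXO-292 dose there is about 1 day in Periods 1, 2 and 4. In Period 3 there are 19 − 14 = 5 days, because Day 7 of Period 2 is study day 14 and Day 1 of Period 3 is study day 19.

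**3. How triglycerides or glucose come to be repeated**

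Under SAP 7.4, a value outside both the reference range and the wider clinical-significance range goes to the investigator, who may request a recheck. Protocol 13.2.6 also allows unscheduled tests. A recheck ordered for another analyte would matter only if it reran the panel, and neither document says whether it does.

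**4. Effect on a mean**

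Let D be the true mean change, f = m/n the share of subjects whose baseline is a non-fasted repeat, and e the non-fasting elevation. Then:

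reported mean change = D − f × e

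All values below are assumptions. That e is positive is also an assumption, not a statement in the documents.

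- One subject, e = 50 mg/dL: 50/12 = 4.2, 50/20 = 2.5 and 50/24 = 2.1 mg/dL too low for n = 12, 20 and 24.
- Two subjects, e = 100 mg/dL, n = 20: 2 × 100/20 = 10 mg/dL too low.
- D = 20, f = 10%: reported 18, 15 or 10 for e = 20, 50 or 100.
- D = 20, f = 25%: reported 15, 7.5 or −5 for the same e.
- Cancelling D = 20 completely needs f = 20/e, which is 40% at e = 50 and 20% at e = 100.

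**5. Effect on one subject's shift**

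Assume an upper limit of 150 and true fasted values of 120 before and 160 after dosing. With the fasted baseline the subject is normal to high, +40. With e = 20 the baseline is 140 and the subject is still normal to high, +20. With e = 50 the baseline is 170 and the subject is high to high, 160 − 170 = −10.

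**6. Direction when a high value prompted the recheck**

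Suppose the scheduled value was high by a chance amount r. The change is D − r from the scheduled value and D − e from the non-fasted recheck. Switching to the recheck moves the change by r − e, which may have either sign.

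**The case against.** A reader might infer that the rule can only hide the named risk. The documents do not support that, for four reasons.

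- **Eligibility rechecks.** Inclusion criterion 4 names liver tests, bilirubin, amylase and lipase. It does not name triglycerides, glucose or cholesterol, so it is not a route unless rechecks repeat the whole panel.
- **The vanishing shift.** A triglyceride recheck requested through the SAP flags for a high result follows a scheduled value already above range. Keeping that value still gives high to high. The example in step 5 needs a panel rerun or an unscheduled draw.
- **Direction.** Step 6 shows that regression to the mean can oppose a meal effect.
- **What remains visible.** Table 14.3.5.1 prints absolute levels at baseline and at each postdose time. The shift table still counts every high scheduled postdose value. Out-of-range values are listed with their rechecks, and values judged clinically significant are reported as adverse events. Safety analysis is descriptive only.

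The exception is also only a permission. Protocol 11.4.2 requires an overnight fast of at least 10 hours before LOXO-292, so a Day 1 morning repeat before any breakfast would meet the 8-hour minimum. The meal listing shell is a placeholder and does not show when repeats are drawn.

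One counter-reading fails. The closing sentence of SAP Section 7 bars rechecks after first dosing from the summaries, which read literally would confine the issue to Period 1. But Section 7 defers to later sections on baseline, and SAP 7.4 expressly allows such values for Periods 2 to 4.

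The asymmetry itself stands: nothing in either document makes a recheck baseline depend on fasting.

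**Conclusion.** The concern holds as a minor weakness in a descriptive analysis. The two documents together let a non-fasted chemistry value into the change and shift tables on the baseline side only, where it can distort the change for triglycerides and glucose. The effect is zero in any treatment column without such a baseline. Under the assumptions in step 4, one or two affected subjects among 20 lower the mean change by 2.5 to 10 mg/dL, and a single subject's shift category may change. The number affected, the elevation and n are all assumed, and the net direction is not established once rechecks of extreme values are allowed for. The point does not support a claim that a triglyceride increase would be missed.

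**What to change.** In SAP 7.4 and in the footnotes of Tables 14.3.5.1 and 14.3.5.2, state: *For triglycerides and glucose, baseline is the scheduled fasted predose sample. A later recheck or unscheduled value replaces it only if that sample is documented as meeting the protocol fast. Non-fasted rechecks are listed with a flag and are not used as baseline.* Leave the current rule in place for other tests.

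The text should say which fasting minimum applies. Protocol 13.2.6 gives 12 hours at check-in, while the footnote to SAP Table 7.4 gives 8 hours for Day -1 of Period 1; these need to be reconciled.

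The cost is one rule and one flag derived from recorded meal and sample times. Subjects are housed only from Day -1 of Period 1, so meals before admission may not be timed. That does no harm, because the scheduled sample is the default and an undocumented repeat simply does not replace it. A few subjects keep the scheduled value instead of the later one. Where that value was extreme by chance, its own regression to the mean stays in the change.

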13.2.7 Adverse Events

13.2.7.1 Adverse Event Definition

An AE means any untoward medical occurrence associated with the use of a drug in humans, whether or not considered drug related.

A suspected adverse reaction means any AE for which there is a reasonable possibility that the drug caused the AE. Reasonable possibility means there is evidence to suggest a causal relationship between the drug and the AE.

An AE can therefore be any unfavorable and unintended sign (including an abnormal laboratory finding), symptom, or disease temporally associated with the use of a medicinal (investigational) product, whether or not related to the medicinal (investigational) product.

13.2.7.2 Monitoring

Subjects will be monitored from screening (signing of informed consent) and throughout the study for adverse reactions to the study drugs and/or procedures. Prior to release, subjects will be asked how they are feeling. At the follow-up, subjects will be queried with an open-ended question such as: 'How have you been feeling since your last visit?'

AEs (whether serious or non-serious) and clinically significant abnormal laboratory test value(s) will be evaluated by the PI or designee and treated and/or followed up until the symptoms or value(s) return to normal, or acceptable levels, as judged by the PI or designee and confirmed by the Sponsor.

Treatment of serious adverse events (SAEs) will be performed by a physician, either at Celerion or at a nearby hospital emergency room. Where appropriate, medical test(s) and/or examination(s) will be performed to document resolution of event(s). Outcome may be classified as resolved, improved, unchanged, worse, fatal, or unknown (lost to follow-up).

13.2.7.3 Reporting

All AEs that occurred during this clinical study will be recorded. The start of the AE reporting for a subject will be the signing of informed consent for this study. Between the time of informed consent and with the first dose of study drug, only AEs (non-serious and serious) assessed as related to study procedures should be reported. All other events should be reported as medical history. After the first dose of study drug, all AEs (serious and non-serious, related and unrelated) should be reported. Unless a subject withdraws consent for follow-up, all subjects must be followed until the end of the AE reporting period at 7 days after the last study drug administration (omeprazole or LOXO-292, whichever comes last) or when any ongoing drug-related AEs and/or SAEs have resolved or become stable. The PI should use appropriate judgment in ordering additional tests as necessary to monitor the resolution of events. The Sponsor may request that certain AEs be followed longer and/or additional safety tests be performed.

The PI or designee will review each event and assess its relationship to drug treatment (yes [related] or no [unrelated]). Each sign or symptom reported will be graded on the National

Institution of Health's Common Terminology Criteria for Adverse Events (CTCAE) version 5.0 toxicity grading scale.

Grade refers to the severity of the AE. The CTCAE displays Grades 1 through 5 with unique clinical descriptions of severity for each AE based on the following general guideline [[CTCAE Nov 2017](#)]:

Grade 1	Mild; asymptomatic or mild symptoms; clinical or diagnostic observations only; intervention not indicated.
Grade 2	Moderate; minimal, local or noninvasive intervention indicated; limiting age-appropriate instrumental ADL*.
Grade 3	Severe or medically significant but not immediately life threatening; hospitalization or prolongation of hospitalization indicated; disabling; limiting self-care ADL**.
Grade 4	Life-threatening consequences; urgent intervention indicated.
Grade 5	Death related to AE.

A Semi-colon indicates 'or' within the description of the grade.

Note: Activities of Daily Living (ADL)

* Instrumental ADL refer to preparing meals, shopping for groceries or clothes, using the telephone, managing money, etc.

** Self care ADL refer to bathing, dressing and undressing, feeding self, using the toilet, taking medications, and not bedridden.

